### 1.3 Clinical Data to Date

Acetazolamide has previously been demonstrated to be efficacious in the treatment of ataxia symptoms in other genetic channelopathies including CACNA1A related disorder (Izquierdo-Serra et al. 2018). Acetazolamide has also been demonstrated to improve the cerebellar symptoms of PMM2-CDG over a six-month pilot study. This initial clinical trial in 24 patients ages 5 to 20 years (mean age  $12.3 \pm 4.5$  years, 9 females, 15 males) demonstrated that acetazolamide is well-tolerated and effective for motor cerebellar syndrome over six months in patients with PMM2-CDG (EudraCT 2017-000810-44). Subjects had statistically significant improvements in ICARS and Nijmegen Pediatric CDG Rating Scale (NPCRS) scores, and lower PATA rates. The PATA rate is the number of “pa – tas” an individual is able to speak in ten seconds. In this study, treatment with acetazolamide coincided with the gain of ability for some patients to sit and stand independently for a longer period of time, which caretakers rated to be an important clinical gain that significantly improved their quality of life and autonomy. Even patients with severe cerebellar atrophy (i.e., low MVRD) showed significant improvement in ICARS, demonstrating a potential therapeutic effect independent of structural cerebellar anomalies and atrophy. In fact, larger gains were observed in individuals with more severe ataxia demonstrated by higher baseline ICARS scores. There were no serious AEs related to the drug during the treatment. There was also no control group comparison, long term follow-up, nor ability to accurately titrate dose by mg/kg. An efficacious dosage of 22 mg/kg/day was established for optimal treatment response, although not all subjects were able to tolerate this dosage, leading to subject drop-out (Martinez-Monseny et al. 2019).

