### **Objective 4 (Secondary):**

**To explore characteristics of individuals with PMM2-CDG who do not respond to acetazolamide.**

In addition to analyzing our data for effect, we will perform subgroup analysis based on genotype, ataxia severity, baseline NPCRS score, sex, concomitant therapies, results of transferrin isoform analysis, concomitant medical problems/diagnoses, number of previous hospitalizations, ages at diagnosis, baseline laboratory test results, age at developmental milestones achievement, baseline developmental/educational achievement, baseline frequency and type of therapies, and baseline support needed for activities of daily living to determine if there are particular subgroups that are less responsive to therapy.

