### 3.4 Primary Study Endpoints

Primary Endpoint: Change in Mini-ICARS score from baseline to 6 months.

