## 7 Statistical Plan

### 7.1 Sample Size Determination

Given that the improvement in ICARS, which is highly correlated to the Mini-ICARS, was 5.6 points over roughly 20 months (Serrano, 2015), if we assume a linear change, then we have  $5.6*(6/20) = 1.68$  points decrease over 6 months. The expected effect size in the experimental group is 6 points decrease, whereas it is 1.68 in the placebo. Using a standard deviation of the change in scores of 4, two-sided alpha 0.05, and power 75%, the sample size required to detect a true difference of 4.32 units is 26 patients total (13 per arm) based on the two-sample t-test.

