#### Primary Endpoint Analysis Approach:

**Primary Hypothesis:** The administration of acetazolamide will improve the ataxia symptoms in patients with PMM2-CDG. **Primary Endpoint:** Change in Mini-ICARS score from baseline to 6 months.

The primary analysis will be conducted using the full analysis set (see Section 7.3). The between-arm mean difference in the change in Mini-ICARS score from baseline to 6 months will be evaluated via a two-sample t-test. The primary analysis will include all patients with a baseline and 6-month Mini-ICARS score. As a sensitivity analysis, all patients with a missing Mini-ICARS score at 6 months will be assumed to have no change in Mini-ICARS score between baseline and 6 months. A per-protocol analysis will also be conducted using the per-protocol set (see Section 7.3). A nominal significance level of  $\alpha=0.05$  will be used for all analyses.

**Exploratory Analysis:** To explore characteristics of individuals with PMM2-CDG who do not respond to acetazolamide (objective 4), we will define the subgroup of individuals who received at least 6 months of acetazolamide and did not have an improvement in ataxia. These individuals could have received acetazolamide during either the blinded period or open label extension period for at least 6 months. In addition, their Mini-ICARS score difference after being on acetazolamide for at least six months was at or less than the mean Mini-ICARS score change for the placebo group. A correlation analysis for change in Mini-ICARS from baseline to 6 months will be performed with each of the baseline characteristics. These baseline characteristics include age, sex, weight, height, head circumference, NPCRS score, Mini-ICARS score, PATA score, concomitant medication list, allergies, current ability with activities of daily living, laboratory

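### Objective 4 correlates Mini-ICARS change with the baseline score contained in that change, so the expected correlation is negative, not zero, even when severity is unrelated to response

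*Combined protocol and SAP*

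**What the plan says.** The exploratory paragraph of Section 7.2 sets out the Objective 4 analysis: "A correlation analysis for change in Mini-ICARS from baseline to 6 months will be performed with each of the baseline characteristics". The list that follows names the baseline value of the outcome scale itself: "These baseline characteristics include age, sex, weight, height, head circumference, NPCRS score, Mini-ICARS score, PATA score". The outcome is the primary endpoint of Section 3.4, "Change in Mini-ICARS score from baseline to 6 months".

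Objective 4 in Section 2 names ataxia severity among its subgroup factors, "to determine if there are particular subgroups that are less responsive to therapy". Section 1.3 reports an earlier signal on this factor from a pilot without a control group: "larger gains were observed in individuals with more severe ataxia demonstrated by higher baseline ICARS scores".

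For this correlation the plan gives no baseline adjustment, no comparison of slopes with placebo, no caution about regression to the mean, and no statement of which patients enter it. A model with baseline as a covariate is planned, but only for the secondary endpoints.

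**The concern.** A reader of the results will take a correlation near zero to mean that severity does not matter, and a clearly negative one to mean that more severe patients gain more (lower Mini-ICARS scores are better). Neither reading is safe when the predictor is part of the outcome. A Visit 1 score that is too high by chance raises the baseline and pushes the change downward. That produces the pattern of larger gains in severe patients without any such relation.

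Two things are at stake. The analysis could appear to confirm the pilot's severity signal through noise. Objective 4 also looks for patients who respond poorly, and if those are the severe patients, the bias works against seeing it.

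**Working it through.** **Inputs from the documents.** Section 7.1: SD of change 4, two-sided alpha 0.05, difference 6 − 1.68 = 4.32, 26 patients (13 per arm). Section 1.3: Cronbach's alpha 0.96 in 13 patients. **Assumed, because not given:** baseline SD of 8 to 15 points, and the share of the change variance that is measurement error.

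**The plan's own figure.** A two-sample t-test with difference 4.32 and SD 4 needs 12.93, so 13 per arm; power there is 75.2%. The stated 26 reproduces. The plan gives no figure for the correlation.

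**Expected correlation when severity is irrelevant.** Let the baseline be X = T + e1 and the 6-month score Y = T + D + e2, with T the true severity and D the true change, independent of T. Then Cov(Y − X, X) = −Var(e), and

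r = −Var(e) / (SD baseline × SD change).

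**Case A: all change variation is noise.** 2 × Var(e) = 4² = 16, so Var(e) = 8. At baseline SD 8, r = −8 / (8 × 4) = −0.25. Simulated rejection of r = 0 at the 5% level (40,000 runs per setting), nearly all in the negative direction:

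| Assumed baseline SD | Null r | 26 patients | 13 patients |
|---|---|---|---|
| 8 | −0.25 | 24% | 13% |
| 10 | −0.20 | 17% | 10% |
| 12 | −0.17 | 13% | 8% |
| 15 | −0.13 | 10% | 7% |

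The 26-patient column treats all patients as one group with a common mean change. If the arms were pooled without adjustment, the 4.32 difference would widen the SD of change to √(16 + 2.16²) = 4.55. At baseline SD 8 the null r would then be −8 / (8 × 4.55) = −0.22, which is slightly smaller.

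**Case B: half the change variance is true variation in response.** Var(e) = 4, so r = −4 / (8 × 4) = −0.125 at baseline SD 8 and −4 / (15 × 4) = −0.07 at SD 15. Rejection with 26 patients is 9% falling to 6%.

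**Case C: reliability 0.96.** Var(e) = 0.04 × SD². At SD 8 this is 2.56 and r = −2.56 / 32 = −0.08; at SD 12 it is 5.76 and r = −5.76 / 48 = −0.12. Rejection with 26 patients is 6.7% at SD 8, 7.7% at SD 10 and 8.7% at SD 12. SD 15 is impossible here, since 2 × 9 = 18 exceeds 16.

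**Masking, under case A.** If improvement truly falls by b points per point of severity, the covariance is b × Var(T) − Var(e). It is zero at b = 8 / (SD² − 8): 8/56 = 0.143 at SD 8, 8/92 = 0.087 at SD 10, and 8/136 = 0.059 at SD 12. A true relation of that size would on average show as no relation. With b = 0.2, error takes 8 of 0.2 × 56 = 11.2 at SD 8, but only 8 of 0.2 × 217 = 43.4 at SD 15, so masking fades as the baseline spread widens.

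**Candidate replacements.** The treatment-by-baseline interaction compares slopes between randomized arms. Visit 1 error precedes randomization and has the same distribution in both arms, so the coupling cancels. With 13 per arm, simulated false positives were 4.9% to 5.1% in every setting. Oldham's method correlates change with the mean of the two scores. Its null covariance is (Var(Y) − Var(X)) / 2 = Var(D) / 2, which is zero in case A but positive whenever true response varies.

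**The case against.** The strongest reply is that case A removes what Objective 4 studies. If the whole SD of 4 is noise, every patient has the same true change and no true non-responders exist. The only reliability evidence in the protocol, alpha 0.96 and near-perfect agreement between three evaluators, also points to small error. This stands as a limit on size: a reader who takes 24% as the expected false-positive rate goes beyond the documents. It does not remove the bias. Internal consistency and agreement between raters do not measure visit-to-visit variation over six months, and the expected correlation is negative in all three cases.

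A reader might also infer that this correlation hides individual severe non-responders. The documents do not support that. Non-responders are classified by a separate rule, a change that "was at or less than the mean Mini-ICARS score change for the placebo group". What the correlation can mask is a trend with severity. The cut-off ignores baseline and so has its own exposure to regression to the mean, which is a different matter.

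The plan also names no null value for the correlation. The usual one is zero, and the preceding paragraph applies 0.05 to all analyses, so that reading is reasonable but inferred. Finally, the analysis is labelled exploratory, is one of dozens of correlations, and the multiplicity paragraph claims strict error control for the primary endpoint only. All of that is right and keeps the point minor.

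**Conclusion.** The point holds as a bias of known direction and uncertain size in one exploratory analysis. With 26 patients, a baseline SD of 8 to 15 and no true relation, the false-positive rate runs from about 6% to 24%. The upper end needs all variation in change to be within-patient noise; the lower figures apply when half the change variance is true response variation or reliability is 0.96. With 13 patients the noise-only range is 13% to 7%. The baseline SD and the test-retest error are assumptions. The floor of the scale, with entry at any score above zero, was not modelled and would add to the bias in the same direction.

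The primary t-test, the sample size of 26 and the primary type I error are untouched. Nor do the documents allow the inference that the pilot's severity finding was itself an artefact; they show only that this analysis could not confirm it.

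**What to change.** In the exploratory paragraph of Section 7.2:

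- Remove baseline Mini-ICARS from the characteristics correlated with raw change. This point does not affect the other listed characteristics.
- State that a raw correlation of change with baseline Mini-ICARS will not be read as evidence that severity predicts response.
- Assess severity with a treatment-by-baseline Mini-ICARS interaction in the randomized blinded-phase data, and report the slope difference with a confidence interval.

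Oldham's method should not be the main replacement. At reliability 0.96, baseline SD 8 and 26 patients it rejects a true null 13% of the time, against 7% for the planned correlation, and it errs toward severe patients responding less.

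The cost is two or three sentences, with no new data or visits, and the change can be made before the blinded-phase data are unblinded. The price is low power for an interaction at 13 per arm, which is why an estimate with an interval is preferable to a test. The interaction also does not remove any real floor effect in mild patients.

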### **Secondary Endpoint Analysis Approach:**

**Secondary Endpoint 1:** Incidence of (a) drug related adverse event(s) and (b) drug related serious adverse event(s) while they are on blinded therapy. The maximum grade for each type of adverse event will be summarized using the CTCAE v5.0. Using the safety set (see Section 7.3), the frequency and percentage of patients with a grade 1+ adverse event or serious adverse event classified as possibly, probably, or definitely related to the study treatment will be summarized by treatment arm. The frequency and percentage of patients who discontinue study treatment due to adverse events will also be reported by treatment arm. This analysis will be repeated to evaluate incidence of (a) drug related adverse event(s) and (b) drug related serious adverse event(s) for the duration that patients remain in the open label extension.

**Secondary Endpoint 2:** PMM2-Biomarker and other scores including:

- carbohydrate deficient transferrin results (Mono/Di, A/Di, Apo CIII1/Apo C III2, Apo CIII0/Apo CIII2),
- electrolytes (Na, K, Cl, CO2),
- VBG (pH, pCO2, PO2, CO2, Base excess) or bicarbonate/CO2,
- liver function tests (AST, ALT, GGT, indirect and direct bilirubin, total protein, albumin, alkaline phosphatase),
- kidney function tests (BUN, Creatinine, Urinalysis, urine calcium/creatinine ratio, urine protein/creatinine ratio),
- growth (height, weight, head circumference),
- vital signs (blood pressure, respiratory rate, heart rate),
- PROMIS scores,
- the PATA score,
- and NPCRS score.

As these endpoints are all numeric, and to identify if the post blinded therapy or final measurement of the open label extension is different from the baseline value, we will use a linear regression model to test if there is a change from baseline. Using the full analysis set (see Section 7.3), the between-arm mean difference in 6-month scores will be evaluated via a linear regression model predicting 6-month scores from baseline scores and treatment arm. This analysis will be repeated based on the final measurement of the open label extension. A nominal significance level of  $\alpha=0.05$  will be used for all analyses.

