### 3.6 Primary Safety Endpoints

The primary safety endpoint is incidence of (a) drug related adverse event(s) and (b) drug related serious adverse event(s) while patients are on blinded therapy as well as for the duration they remain in the open label extension.

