### 3.7 Identification of Source Data

The following data will be collected:

- Date of visit
- Age at visit (Years, Months, Days)
- Vital signs: systolic and diastolic blood pressures (mmHg), heart rate (beats/minute), respiratory rate (breaths/minute), temperature (degrees C)
- Growth Data: length/height (cm), weight (kg), head circumference (cm)
- Physical Exam: brief neurologic exam, cardiovascular exam, abdominal exam, (HEENT) head ears eyes nose throat exam, dermatologic exam, pulmonary exam, musculoskeletal exam (Normal/Abnormal with text field to explain abnormality)
- PATA score
- AE and SAEs defined by the CTCAE version 5 (specific AE/SAE and date; see Appendix D)
- PROMIS Questionnaires (Appendix C)
- Mini-ICARS (Appendix B)
- NPCRS (Appendix A)
- Drug volume prescribed (ml/day or number of capsules/day)
- Laboratory values, normal ranges, and units: CBC (WBC, Hgb, Hct, Plt, % Neutrophils, % Lymphocytes, % Eosinophils, % Basophils, % Monocytes, % Bands, MCV, MCHC, MCH), electrolytes (Na, K, Cl, CO2), VBG (pH, pCO2, PO2, CO2, Base excess) or bicarbonate/CO2, liver function tests (AST, ALT, GGT, indirect and direct bilirubin, total protein, albumin, alkaline phosphatase), coagulation factors (prothrombin time, coagulation factor XI, and antithrombin), kidney function tests (BUN, Creatinine, Urinalysis, urine calcium/creatinine ratio, urine protein/creatinine ratio)
- BSAP, CTX, calcium, phosphorus, vitamin D, and PTH at baseline and visit 5.
- Plasma/Serum Acetazolamide level at visit 5.
- Physical therapy, Occupational therapy, Speech therapy, Feeding therapy – (yes/no if ongoing, number of sessions per month)
- Annual screening ophthalmological exam including intraocular pressure testing.

The following source data will be captured in supportive documentation (e.g. study source documents, EMR):

- Clinical interpretation of laboratory values
- Medication review and adherence
- Video of the Mini-ICARS assessment

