### Adverse Event Reporting Period

The study site will document all AEs that occur (whether or not related to study drug) within one week of the investigator becoming aware of the event. The collection period for all AEs will begin after informed consent is obtained and end after procedures for the final study visit have

been completed. In accordance with the standard operating procedures and policies of the local Institutional Review Board (IRB), the site investigator will report SAEs to the IRB.

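### AE and SAE incidence by arm is planned only for events judged drug-related; an all-cause comparison from data already collected is missing

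*Combined protocol and SAP*

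**What the plan says.** Collection is unrestricted. Under Adverse Event Reporting Period in 8.1: "The study site will document all AEs that occur (whether or not related to study drug").

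The endpoint is restricted. Section 3.6 defines the primary safety endpoint as "incidence of (a) drug related adverse event(s) and (b) drug related serious adverse event(s"), in the blinded phase and in the extension. Objective 2 in section 2 is framed the same way.

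The analysis follows the endpoint. Section 7.2, Secondary Endpoint 1, uses the safety set and tabulates by arm "patients with a grade 1+ adverse event or serious adverse event classified as possibly, probably, or definitely related to the study treatment". Two further outputs sit in the same paragraph:

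- "The maximum grade for each type of adverse event will be summarized using the CTCAE v5.0". Neither an arm split nor a relatedness condition is stated.
- The frequency and percentage of "patients who discontinue study treatment due to adverse events will also be reported by treatment arm". This carries no relatedness condition.

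Secondary Endpoint 2 separately compares laboratory values, growth and vital signs between arms, using the full analysis set. Neither 7.3 nor 8.6.1 adds an all-cause incidence table by arm.

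**The concern.** In a placebo-controlled trial, the harm comparison that randomisation protects is the one that counts every event. Filtering on relatedness puts a human judgement, made after treatment has started, between the randomised groups and the table. If that judgement is affected by anything that differs between arms, the table can show an excess that is not there. If investigators put a drug effect down to the underlying disease, the table can lose an excess that is there.

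Both routes are plausible here. Low bicarbonate is an expected effect of acetazolamide and feeds the dose rules in 5.2, so laboratory-driven dose changes should fall mainly on active drug. Ataxia is listed in 1.5 as a possible side effect and in 1.1 as a core feature of PMM2-CDG. At stake is the reading of tolerability in a small trial that 1.5 describes as possible groundwork for a labelled indication.

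**Working it through.** **Scale.** The plan gives no figure for AE incidence or attribution, so there is none to reproduce. The arm size does reproduce: with a difference of 6 − 1.68 = 4.32, SD 4 and two-sided alpha 0.05, the t-test has power 0.752 at 13 per arm (0.715 at 12), against the stated 75%. Allowing for 20% loss, 26/0.8 = 32.5, which rounds up to the stated 33. I use 13 per arm for scale.

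**What is compared between arms, and through which filter**

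| Output (7.2) | Relatedness filter | By arm |
|---|---|---|
| AE and SAE incidence | Yes, possibly or above | Yes |
| Discontinuation due to AEs | No | Yes |
| Maximum grade per AE type | None stated | Not stated |
| Laboratory values, growth, vital signs | No | Yes, full analysis set |
| All-cause AE or SAE incidence | – | Not planned |

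**Can dose information reach the person judging causality?** Section 5.2 has bicarbonate and pH monitored by a clinician outside the study, and 6.2 to 6.4 have a partnering clinician give the blinded-phase dose instruction. Against that:

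- Section 3.7 lists "Drug volume prescribed (ml/day or number of capsules/day") and bicarbonate among the study data, and 9.3 has the site coordinator or the investigator enter site data.
- Section 8.3 has the investigator evaluate each event. Table 5 builds the response to stopping or reducing the dose into Definitely and Probably, so applying the scale needs knowledge of dose changes.
- Section 3.1 adjusts placebo capsules on the patient's own symptoms and laboratory values. No sham reductions are described.

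**Illustration of a spurious excess.** Let p be the true any-AE risk, equal in both arms. Let c be the probability of a dose cut known to the assessor, a1 the probability that an event is called related after a cut, and a0 the probability without one. Treating each patient with an AE as having one event:

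Related incidence = p × [c × a1 + (1 − c) × a0]

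Excess on active = p × (c_active − c_placebo) × (a1 − a0)

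The only input from the documents is c_active. The table of published studies before 1.5 reports abnormally low bicarbonate in 9 of 24 pilot patients, or 37.5% (exact 95% CI 18.8% to 59.4%). Using it as the share with a known cut is an assumption, and so are p, a0, a1 and c_placebo.

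| p | a0 | a1 | c_placebo | Active | Placebo | Excess (points) | Patients of 13 |
|---|---|---|---|---|---|---|---|
| 0.60 | 0.50 | 0.50 | 0 | 30.0% | 30.0% | 0 | 0 |
| 0.60 | 0.50 | 0.60 | 0 | 32.25% | 30.0% | 2.25 | 0.3 |
| 0.40 | 0.50 | 0.80 | 0.05 | 24.5% | 20.6% | 3.9 | 0.5 |
| 0.60 | 0.50 | 0.80 | 0 | 36.75% | 30.0% | 6.75 | 0.9 |
| 0.80 | 0.30 | 0.90 | 0 | 42.0% | 24.0% | 18.0 | 2.3 |

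For the fourth row, 0.60 × (0.375 × 0.80 + 0.625 × 0.50) = 0.3675. Moving c_active to its confidence limits gives 0.60 × 0.188 × 0.30 = 3.4 points and 0.60 × 0.594 × 0.30 = 10.7 points. The last row is an extreme. An all-cause table shows no difference in any row.

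**Illustration of masking.** If a fraction q of events of some type is called related in both arms, a true excess D appears as q × D. At q = 0.5 half of it is lost, and at q = 0.3 only 30% remains. This needs no unblinding.

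**Precision.** The 95% half-width for a difference at 13 per arm is 1.96 × √(2 × 0.3 × 0.7/13) = 35 points at 30% incidence, and 38 points at 50%.

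**The case against.** The strongest reply is that the plan guards against this, that the bar for relatedness is low, and that any effect is lost in noise. Several parts of that reply stand.

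- **The safeguard is real.** A reader might infer that dose cuts are openly visible to the assessor and that the comparison is therefore arm-dependent. The documents do not say so. Visibility is inferred from data entry and from Table 5, against an explicit arrangement meant to prevent it.
- **Low bicarbonate is not the same as a dose cut.** In 5.2, one bullet keeps the dose where pH is at least 7.3 and/or bicarbonate is below 21, and another reduces or stops it where pH is below 7.3 and/or bicarbonate is below 21. These must be reconciled, and until then the share with a cut is unknown. The pilot entry gives no threshold for abnormally low, and placebo capsules can also be adjusted.
- **Timing limits the effect.** The laboratory-driven reduction in 5.2 applies when no related or likely related AE is present, so mainly later events could be influenced.
- **The bar for Possibly is low.** In Table 5, Unrelated requires certainty. The dechallenge element separates Probably from Possibly, and both pass the filter. If a0 is 0.90, the excess cannot exceed 0.60 × 0.375 × 0.10 = 2.25 points.
- **Not all harm information passes through the filter.** A reader might infer that it does. Discontinuations and the laboratory, growth and vital-sign comparisons do not, and 8.6 sends every SAE to the DSMB.

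These points weaken the size and certainty of the first route. They do not supply the missing table. Discontinuation captures only events that ended treatment, the laboratory comparisons are limited to patients with both visits, and DSMB review is not a reported comparison. The masking route is unaffected by the blinding safeguard. That related events are the stated endpoint justifies keeping their table, not omitting the all-cause one.

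**Conclusion.** The point holds as a reporting gap of moderate weight. AE and SAE incidence by arm is planned only for events judged related, although all AEs are collected, and no all-cause incidence by arm is specified.

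The judgement could be influenced by dose changes expected mainly on active drug, and it could remove drug effects that look like the disease. The documents establish neither that this will happen nor how much. The size rests on assumed attribution rates, on the pilot's 37.5% standing in for known dose cuts, and on one event per patient. On that footing it is a few percentage points, roughly 0 to 2 of 13 patients, well inside the sampling error of 35 to 38 points, and zero if attribution ignores dose changes. The claim that the related-only table will show a false excess is therefore not supported. That the plan leaves out a comparison which does not depend on attribution is supported.

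The primary efficacy analysis and the sample size are unaffected.

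**What to change.** In 7.2, Secondary Endpoint 1, add for the blinded phase:

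*On the safety set, the number and percentage of patients with any AE, any grade 3 or higher AE and any SAE, regardless of relationship to study treatment, will be presented by treatment arm, overall and by event type. A risk difference with an exact 95% CI will be given for the overall rows only. Maximum grade per AE type will be summarised by treatment arm.*

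Keep the related-only table, since it serves the endpoint in 3.6, and state that it will be read alongside the all-cause table. Limiting intervals to the overall rows avoids a long list of very wide ones at about 13 per arm. Make the change before the blinded-phase database is unblinded, so that the choice of safety table is not post hoc.

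The cost is a few lines of SAP text and one extra table from data already collected. The downside is that all-cause rates include background disease events, so they will be higher and noisier.
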